6.5 Blinding and Allocation/Randomization

Blinding

Property of GSK Consumer Healthcare - Confidential

May not be used, divulged, published or otherwise disclosed without the consent of GSKCH

This study is described as single blind or examiner-blind (the examiner performing the bite force evaluation will be blinded to the product received). Other staff from the study site will not be blinded to treatment received.

To ensure the examiner performing the bite force evaluation remains blinded throughout the study, staff involved in the preparation and dispensing of study products will work in a separate area.

The investigator's knowledge of the product allocation should not influence the decision to enroll a subject or affect the order in which subjects are enrolled.

Randomization

All subjects will be randomized according to the randomization schedule provided by the study biostatistician at PPD. Before the study is initiated, training, login information and directions for Study products will be dispensed according to the randomization schedule at the appropriate study visits. Returned study products should not be re-dispensed to any subject.

A unique screening number will identify each subject screened for study participation. Screening numbers will be assigned in ascending numerical order as each subject signs their consent form. Subjects who meet all inclusion and exclusion criteria will be randomized according to the randomization schedule. Randomization numbers will be assigned in ascending numerical order as each subject is determined to be fully eligible. The randomization schedule will indicate the treatment order sequence; one of the three treatments or no adhesive (negative control) to be used for each of the four study periods. The randomization will use a Williams Square layout appropriate for a 4-period crossover study. The study site will receive one randomization schedule with de-coded treatments. This schedule will be used to dispense study treatments to the subjects.

6.6 Breaking the Blind

In case of an emergency, the investigator has the sole responsibility for determining if unblinding of a subject's product assignment is warranted. Subject safety must always be the first consideration in making such a determination. If the investigator decides that unblinding is warranted, the investigator should make every effort to contact the sponsor prior to unblinding a subject's product assignment unless this could delay emergency treatment of the subject.

If a subject's product assignment is unblinded, the sponsor must be notified within 24 hours after breaking the blind. The date and reason that the blind was broken must be recorded in the source documentation and case report form, as applicable.

Any AE associated with breaking the blind must be recorded and reported as specified in this protocol. The study site may also be required to inform the IRB/EC if the blind is broken.

To break the blind, the study coordinator will use the randomization schedule to inform the investigator of the treatment assignment for the subject for the appropriate study visit.

6.7 Compliance

Study products will be administered by investigator site personnel.

The number of any missed or additional applications will be captured as protocol deviations into the CRF.

6.8 Concomitant Medication/Treatment(s)

Any medications, treatments or vaccine (including over-the-counter or prescription medicines, vitamins, and/or herbal supplements) taken during the study, from signing the informed consent, must be recorded in the CRF with indication, reason for use, unit dose, daily dose, and start and stop dates of administration. All subjects will be questioned about medications/treatments at each site visit.

Details of any relevant dental, medical or surgical history (within the last year), including allergies of drug sensitivity, will be recorded in the CRF. The use of concomitant medications is permitted in this study except for the use of bisphosphonate drugs ([exclusion criterion 9](#)) and any medications that in the opinion of the investigator would interfere with the conduct of this study ([exclusion criterion 10](#)).

Medication/treatments taken within 7 days of signing the informed consent form will be documented as a prior medication/treatment. Medications/treatments taken after application of first treatment (test adhesives or no adhesive as per randomization schedule) will be documented as concomitant medication/treatments.

Subjects will be instructed not to have any non-emergency dental/denture work performed during the time they are in the study, unless discussed and permitted by the examiner. This is to assure that the denture fit will not be altered during the study.

7 DISCONTINUATION OF STUDY INTERVENTION AND SUBJECT DISCONTINUATION/WITHDRAWAL

7.1 Subject Discontinuation/Withdrawal

A subject may withdraw from the study at any time at his or her own request or may be withdrawn at any time at the discretion of the investigator or sponsor for safety, behavioral reasons, or the inability of the subject to comply with the protocol required schedule of study visits or procedures.

The following circumstances require discontinuation of study product and/or premature subject withdrawal:

- Protocol violation that may impact the subject's safety
- Withdrawal of informed consent
- Subject lost to follow-up
- Pregnancy

If a subject is discontinued or prematurely withdraws from the study, the reason(s) for discontinuation or withdrawal and the associated date must be documented in the relevant section(s) of the CRF.

7.2 Lost to Follow up

If a subject fails to return to the site for a required study visit the site must attempt to contact the subject and reschedule the missed visit as soon as possible and counsel the subject on the importance of maintaining the assigned visit schedule and ascertain whether the subject wishes to and/or should continue in the study.

A subject will be considered lost to follow up if he or she repeatedly fails to return for scheduled visits and is unable to be contacted by the study site. Before a subject is deemed lost to follow up, the investigator or designee must make every effort to regain contact with the subject (where possible, 3 telephone calls and, if necessary, a certified letter to the subject's last known mailing address or local equivalent methods). These contact attempts should be documented. If contact is made with the subject, the investigator should inquire about the reason for withdrawal, request that the subject return all products that they had been dispensed and if appropriate request that the subject return for a final visit and follow-up with the subject regarding any unresolved adverse events (AEs).

Final safety assessments may be carried out when the subject returns to the study site, at the investigator's discretion, which may include an OST examination.

Should the subject continue to be unreachable, he/she will be considered to have withdrawn from the study and lost to follow up.

Lack of completion of all or any of the early termination procedures will not be viewed as protocol deviations so long as the subject's safety was preserved.

If the subject withdraws from the study and withdraws consent for disclosure of future information, no further evaluations should be performed, and no additional data should be collected except for any pertinent safety information. The sponsor may retain and continue to use any data collected before such withdrawal of consent.

8 STUDY PROCEDURES

This section lists the procedures to be completed at each planned study visit. The timing of each procedure is listed in the Schedule of Activities section.

Adherence to the study design requirements, including all procedures are essential and required for study conduct.

8.1 Visit 1/Screening

Screening procedures will be conducted by the Investigator, or suitably qualified designee.

Subjects will be screened within 1-28 days prior to administration of the treatment (test adhesive or no adhesive as per randomization schedule) to confirm that they meet the subject selection criteria for the study.

The following procedures will be completed in the order specified where possible and the outcomes recorded in the CRF:

- Informed consent
- Medical history and prior and current medications/treatments
- Dental history
- Inclusion/exclusion criteria assessment
- Demographics
- Current/prior/concomitant medication review
- Maxillary denture cleaning
- Kapur-Olshan Index (well-fitting assessment) only for maxillary dentures.
- Well-made assessment for maxillary dentures, and mandibular dentures if present.
- OST examination prior to denture adhesive application (if required for mandibular stabilization) and/or commencement of BF measurements.

Property of GSK Consumer Healthcare - Confidential

May not be used, divulged, published or otherwise disclosed without the consent of GSKCH

- OHT examination
- Mandibular denture cleaning followed by stabilization (if present)
- Perform BF training bites and qualifying bites
- Subject eligibility assessed
- Removal of denture and excess adhesive from mouth (used for mandibular stabilization)
- OST examination post mandibular denture and denture adhesive removal
- Post BF assessment denture cleaning
- Adverse events and medical device incidents review

8.1.1 Informed Consent

The investigator, or designee, must obtain informed consent from each subject participating in this study after adequate explanation of the aims, methods, objectives, and potential hazards of the study. The informed consent form (ICF) will be signed and dated by the subject, the subject will receive a copy and the original will be kept at site.

The investigator, or designee, must also explain to the subjects that they are completely free to refuse to enter the study or to withdraw from it at any time. Appropriate forms for documenting a signed and dated consent will be provided by either the investigator or by GSK CH.

The investigator, or designee, should sign and date each copy of the ICF to confirm that the consent process was completed correctly after the subject has signed.

The time the subject signed the informed consent form will be documented in the CRF as this is the point from which all Adverse Events will be captured.

If, during a subject's participation in the study, any new information becomes available that may affect the subject's willingness to participate in the study, each ongoing subject should receive a copy of this new information and be re-consented into the study. Each subject should be provided with a copy of the signed and dated amended consent form. The date of re-consent will be recorded on the CRF.

After signing the ICF, subjects will undergo the screening assessments to confirm that they meet all the inclusion criteria and none of the exclusion criteria. If the subject is confirmed eligible by the investigator (or designee) to participate in the study the subject is considered enrolled in the study.

8.1.2 Medical History and Prior Medication/Treatment

Details of relevant medical and surgical history (in the last 1 year), including allergies or drug sensitivity, will be documented in the CRF.

Prior medications/treatments, including prescription and non-prescription drugs, dietary supplements and herbal remedies, taken in the last 7 days and prior to signing the informed consent form, will be documented in the CRF.

8.1.2.1 Dental History

The investigator, or medically qualified designee will take a dental history from each subject at the Screening visit. Dental history will include information of all prostheses in the mouth, maxillary and mandibular, as well as information regarding the age of dentures, how long the subject has worn dentures, the prosthetic material and whether the subject is a regular user of denture adhesives. This will be documented in the CRF.

8.1.3 Inclusion/Exclusion Criteria

Inclusion and exclusion criteria information will be documented in the CRF.

The well-fitting and well-made and the OST assessments should be performed by suitably qualified personnel/examiner with expertise in prosthodontics. The bite force assessments should be performed by an assessor appropriately trained in the technique.

8.1.4 Demographics

The following demographic information will be recorded in the CRF: year of birth, gender, race and ethnicity.

Ethnicity and race of subjects will be recorded in accordance with FDA Guidance for Industry: Collection of Race and Ethnicity Data in Clinical Trials, 2005. This is required for this study as the experimental denture adhesives being tested are intended to be marketed in the US.

Descriptive statistics (number of subjects, mean, standard deviation (SD), median, minimum and maximum for continuous variables, and frequency and percentage for categorical variables) will be provided for demographic and baseline data.

8.1.5 Denture Cleaning

Wearing gloves, denture cleaning will be performed by suitably qualified site staff. Sufficient denture cleaning paste will be applied to the supplied denture brush. All surfaces of the denture(s) will be thoroughly cleaned to remove all visible traces of denture fixative, plaque and particulate/debris. The denture(s) will then be rinsed thoroughly with running water.

Denture(s) should then be dried using clinical paper towels. Denture cleaning paste should only be used extra-orally and not directly in the mouth. Hands should be washed thoroughly following application and use of the denture cleaning paste. If a subject has two full dentures, both maxillary and mandibular dentures should be cleaned prior to treatment application or prior to denture insertion if subject is randomized to no adhesive group. The denture cleaning paste and/or warm water can be used to clean the dentures at the end of the day at the examiner's discretion.

8.1.6 Mandibular Denture Stabilization

Prior to all bite force measurements, any mandibular denture (partial or complete) will be fully stabilized using the supplied denture adhesive, to ensure accuracy of BF measurements. The mandibular denture will be thoroughly cleaned as per [Section 8.1.5](#) before adhesive application. The denture adhesive will be applied in accordance with label instructions and will not be controlled by weight to ensure the mandibular denture is securely held in place to avoid interfering with maxillary BF measurements. The mandibular denture may be re-stabilized a further 2 times throughout the test day (maximum of 3 three applications per day) at the examiner's discretion.

8.1.7 Subject Eligibility

The investigator and/or medically qualified designee will review inclusion/exclusion criteria, medical history, prior medications to confirm subject eligibility to participate in the clinical trial. This will be documented in the CRF.

To prepare for study participation, subjects will be instructed in the [Lifestyle Guidelines](#) and any [Concomitant Medication/Treatment\(s\)](#) requirements of the protocol.

Once subject eligibility is confirmed against screening inclusion/exclusion criteria, study specific screening tests will be carried out. These include the Kapur Olshan Index assessment, criteria for well-made and fitting dentures, OST exam and BF assessments for training and qualifying bites on the BF transducer. Details of each of these assessments are given in [Section 9.1.4](#). All assessments will be documented in the CRF.

8.2 Study Period

8.2.1 Visits 2-5/ Treatment Periods 1-4

There will be a washout period of a minimum of 1 day (max 28 days) between treatment visits. The following procedures/ assessments will take place in the order listed below as much as possible and recorded in the CRF:

- Review of concomitant medications and non-drug treatments/procedures and lifestyle restrictions
- Review of inclusion/exclusion criteria
- OST examination prior to denture adhesive application
- Mandibular denture cleaning followed by stabilization (if present)
- BF measurement - practice bites
- BF measurement- pre-treatment baseline incisal BF measurement
- Subject continuance assessed and confirmed
- Randomization (only at Visit 2, Treatment period 1)
- Product application (for subjects randomized to an adhesive treatment arm). For subjects randomized to no adhesive, the maxillary denture will be cleaned, dried and re-fitted into subject's mouth.
- BF assessment at 0.5hrs
- BF measurement at 1hr
- BF measurement at 3hrs
- BF measurement at 6hr
- BF measurement at 9hr
- BF measurement at 12hr
- Removal of denture(s) (by either site staff or subject) and excess adhesive from mouth (by site staff) once all bite force assessments completed
- OST examination post denture and denture adhesive removal
- OHT examination (only at Visit 5, Treatment period 4)
- Post-testing denture cleaning
- Adverse events and medical device incidents review
- Study conclusion (only at Visit 5/Treatment period 4)

All procedures and assessments are detailed in [Section 9](#).

Changes in concomitant medication or non-drug treatments/procedures will be documented in the CRF.

Spontaneous reporting of adverse events and those elicited by asking subjects to respond to a non-leading question such as "How do you feel?" will be assessed and any AEs recorded in the CRF.

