1.2 Schedule of Activities

The schedule of activities table provides an overview of the subject visits and study procedures.

The investigator may schedule visits (unplanned visits) in addition to those listed on the schedule of activities, to conduct evaluations or assessments required to protect the well-being of the subject.

Table 1-1 Schedule of Activities

Procedure/Assessment	Screening	Study Period							
	Visit 1		Visit 2 Treatment Period 1		Visit 3 Treatment Period 2		Visit 4 Treatment Period 3		Visit 5 Treatment Period 4
Informed consent	X								
Medical history	X	Between 1 and 28 days							
Dental history	X								
Demographics	X								

Property of GSK Consumer Healthcare - Confidential

May not be used, divulged, published or otherwise disclosed without the consent of GSKCH

Procedure/Assessment	Screening		Study Period						
	Visit 1		Visit 2 Treatment Period 1		Visit 3 Treatment Period 2		Visit 4 Treatment Period 3		Visit 5 Treatment Period 4
Current/prior/concomitant medication review	X		X		X		X		X
Denture cleaning ⁶	X		X		X		X		X
Denture Bearing Tissue Assessment	X								
Criteria for well-made and fitting dentures	X								
Kapur-Olshan Index assessment to determine eligibility	X								
Inclusion/exclusion Criteria	X		X		X		X		X
OST Examination ¹	X		X		X		X		X
OHT Examination ²	X								X
Mandibular denture stabilization ³	X		X		X		X		X
Training bites (3 incisal BF measurements with no adhesive)	X								
Qualifying bites (4 Incisal BF measurements with no adhesive)	X								
Subject eligibility	X								
Practice bites (3 Incisal BF measurements with no adhesive)			X		X		X		X
Baseline (pre-treatment) incisal BF measurements			X		X		X		X
Subject continuance			X		X		X		X
Randomization			X						
Product application to maxillary denture by site staff			X		X		X		X
Incisal BF measurements (0.5, 1, 3, 6, 9, 12hr)			X		X		X		X
Denture cleaning at end of study visit day with removal of excess adhesive from mouth ⁴	X		X		X		X		X
Adverse events and incidents review ⁵	X		X		X		X		X
Study conclusion/subject exit from study									X

Abbreviations: OST: Oral Soft Tissue, OHT: Oral Hard Tissue, BF: Bite force

Footnotes:

1. OST exam performed before denture stabilization (if required) and/or commencement of BF assessments; and again after denture and residual adhesive removal at end of each study visit.

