On each test day (Visit 2 to Visit 5) subjects will return to site without denture adhesive being used, where subject continuance will be assessed and confirmed, an OST-edentulous examination performed. Subject's dentures will then be cleaned, the mandibular denture will be stabilized (as required) and the subject will rinse their mouth with potable water prior to placement of the dentures in the mouth. Subjects will then perform 3 practice bites to re-familiarize them with the BF transducer and then they will undergo the baseline incisal BF measurement (the different bites are summarized in Table 4-1). Following randomization, for subjects randomized to use of an adhesive, 1.0g (± 0.05 g) adhesive product will be applied only to the maxillary denture as per the application instructions (Appendix 1), and the subject will refit their denture. For subjects randomized to no adhesive use, the clean and dried denture will be refitted without adhesive.

Table 4-1 Incisal Bite Force Descriptions

Bite	When Performed	Purpose
Training	Screening, Visit 1	3 bites to familiarize subjects with BF equipment and performing a bite.

Property of GSK Consumer Healthcare - Confidential

May not be used, divulged, published or otherwise disclosed without the consent of GSKCH

Bite	When Performed	Purpose
Qualifying	Screening, Visit 1	4 bites that must equal ≤ 9 lbs with 2 of these bites within (± 2 lb) as part of inclusion criteria.
Practice	Test days (Visit 2-5) pre baseline measurements and adhesive application	3 bites to re-familiarize subjects with performing valid bite.
Baseline	Test days (Visit 2-5) pre adhesive application	A single bite to determine Baseline measurement without adhesive application. Must be ≤ 9 lbs and within ± 2 lbs of one of the practice bites performed on the same day.
Test	Test days (Visit 2-5) following adhesive application	Single test bites taken at 0.5, 1, 3, 6, 9 and 12hrs.

Test incisal BF measurements will be taken at 0.5, 1, 3, 6, 9 and 12 hrs (± 5 mins for the 0.5 hr measurement, ± 10 mins for all other time points) after denture refitting. Following the 12hr incisal BF measurements, the dentures, and any excess adhesive will be removed, and the dentures will be cleaned before returning to the subject after a further OST- examination.

Safety will be monitored throughout the study through the reporting of AEs, incidents and OST/OHT examination. The examiner performing the BF assessment should remain blinded to the treatment.

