6.2 Administration

Subject's dentures will first be cleaned to remove all traces of denture fixative, plaque and particulates/debris then and dried prior to application of randomized adhesive [\(Section 8.1.5\)](#). For subjects randomized to no adhesive, the cleaning will still be performed in order to standardize the cleanliness of the denture prior to commencement of the BF testing. Both maxillary and mandibular (if present) dentures should be cleaned.

Experimental and positive control adhesives will be applied to maxillary denture directly from the product packaging onto the dentures as per the Product Application Instructions ([Appendix 15.2](#)). The dentures will then be returned to the subject who should reposition the dentures in their mouth and bite down to secure hold. For subjects randomized to no adhesive, the dentures should refitted by the subject following cleaning and drying.

Only subjects enrolled in the study may receive study products and only authorized site staff may supply or administer study products. All study products must be stored in a secure, environmentally controlled, and monitored (manual or automated) area in accordance with the labeled storage conditions with access limited to the authorized site staff only.

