9.2 Efficacy Assessments

The following efficacy assessments will be performed by appropriately trained staff/clinical examiners, at the times and in the order defined (as much as possible) in the [Study Procedures](#) section of this protocol.

If in the opinion of the examiner a subject is between defined grades/scores, a conservative approach should be used to provide the final score. The same approach should be applied throughout the study to ensure consistency in the grading of the scores at all timepoints.

9.2.1 Treatment Day (Visits 2-5) Maxillary Bite Force Assessments (Practice, Baseline and Test Bites)

All BF measurements will be conducted by an examiner (preferably by the same examiner throughout the study) that is fully trained in the use of the BF transducer equipment and is experienced in performing BF measurements. Prior to any BF measurements on treatment days (Visit2-5) the mandibular dentures, if present, will be stabilized ([Section 9.1.4](#)).

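### Does the Visits 2-5 procedure list allow the baseline bite to be taken on an uncleaned maxillary denture?

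*Protocol*

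**What the plan says.** Protocol 4.1 sets out each test day as a sequence. After the soft tissue examination, "Subject's dentures will then be cleaned, the mandibular denture will be stabilized (as required"). The mouth rinse, placement of the dentures, three practice bites and the baseline bite come next. Every subject wears a full maxillary denture, so the plural covers it.

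Protocol 8.2.1 gives the same visits as an ordered list. The only cleaning above the bites is "Mandibular denture cleaning followed by stabilization (if present"). The upper denture first appears after the baseline, the continuance check and randomization, inside the product application item: "For subjects randomized to no adhesive, the maxillary denture will be cleaned, dried and re-fitted into subject's mouth". The screening list in 8.1, by contrast, carries "Maxillary denture cleaning" as its own item ahead of the screening bites.

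Other places bear on the timing:

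- Section 8 states that "The timing of each procedure is listed in the Schedule of Activities section". In Table 1-1 the denture cleaning row, marked for Visits 2-5, stands above the row "Practice bites (3 Incisal BF measurements with no adhesive").
- Footnote 6 to that table and Section 8.1.5 link cleaning to product application or denture insertion and do not mention the baseline bite.
- Section 9.2 has efficacy assessments done "at the times and in the order defined (as much as possible") in the Study Procedures section.
- Section 6.2 gives the purpose of cleaning as "in order to standardize the cleanliness of the denture prior to commencement of the BF testing".

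**The concern.** A site that works from 8.2.1 alone finds no instruction to clean the upper denture before the baseline bite. For a subject with natural lower teeth it finds no cleaning before baseline at all. Section 5.5.3 lets habitual users keep using their own adhesive between visits, so some residue on arrival is possible.

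The baseline does three jobs. It is subtracted to form AOB, it supplies both covariates in the ANCOVA (subject-level baseline, and period-level minus subject-level baseline), and it decides continuance through the 9 lb ceiling and the 2 lb agreement rule. If residue raised the baseline, the test bites, which follow cleaning, would be compared with a baseline taken under a different condition. The 9 lb limit would apply to a cleaned denture at screening and to a possibly uncleaned one later. Some subjects might also be discontinued who would otherwise have stayed. The plan randomizes at least 45 to obtain 42 completers, a margin of three.

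**Working it through.** **1. Do the passages conflict?** Section 4.1 requires cleaning before the bites. Section 8.2.1 is silent about the upper denture at that point. Silence is not a contrary instruction: a site can do everything in 4.1 and everything in 8.2.1 on the same day, and the list order binds only as far as practicable. Footnote 6 and 8.1.5 fit either order. The row order of Table 1-1 is weak support only, because the table also puts cleaning above the soft tissue examination, which 4.1 places first.

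Two other rules limit what could be on the denture. Subjects report without adhesive on either denture (4.1, 5.5.3), and the baseline is by definition taken with no adhesive (9.2.1.2, inclusion criteria 6c and 6d). What remains is trace residue in habitual users, at a site that ignored 4.1. Test bites follow cleaning in every arm: step 1 of 15.2.1 and 15.2.2 for the adhesives, the refitting item in 8.2.1 for no adhesive.

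**2. Weight of the baseline in AOB0-12.** In the trapezoid rule the first interval is 0 to 0.5 h, so baseline enters AUC with weight 0.25. Its net coefficient is 0.25/12 − 1 = −0.979. With test bites unchanged, a 1 lb lift in one period lowers that period's unadjusted AOB0-12 by 0.98 lb.

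**3. Reference precision (Protocol 12.1).** With n = 42 and residual SD 2.83 lb, the SE of a treatment difference is 2.83 × √(2/42) = 0.618 lb. With delta 2.30 lb and the SAP's testing scheme (positive control at 5%, two Dunnett-adjusted tests, critical value 2.24), simulation gives a probability of study success of about 0.94. This is consistent with the stated 90%.

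**4. Effect of residue on the SE.** The documents give no residue size, frequency or baseline distribution. The following are assumptions:

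- a lift L in a random half of subject-periods, independent of treatment
- a visit-to-visit SD of the clean baseline of 1.0 or 1.5 lb
- 0, 50 or 100% of that variation carried into later bites
- subject-level baseline taken as the mean of the subject's period baselines

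The worst case is SD 1.5 lb with full carry-over, because the covariate then cannot separate lift from true variation. The lift variance is L²/4. The part the covariate leaves is 2.25 × (L²/4) / (2.25 + L²/4).

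| Lift | Part left (lb²) | Residual SD (lb) | Ratio to 2.83 |
|---|---|---|---|
| 2 lb | 2.25 × 1 / 3.25 = 0.692 | √(8.009 + 0.979² × 0.692) = 2.945 | 1.04 |
| 4 lb | 2.25 × 4 / 6.25 = 1.44 | √(8.009 + 0.979² × 1.44) = 3.064 | 1.08 |

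A simulation of the planned model (8,000 trials per scenario) agrees. The mean SE is 0.618-0.620 without residue, 0.620-0.646 at 2 lb and 0.620-0.672 at 4 lb. Mean estimates stay between 2.29 and 2.31 against a true 2.30. With no carry-over the SE does not rise.

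**5. Effect on study success.** Repeating the calculation in step 3 with the worst SEs gives 0.92 at 0.646 and 0.90 at 0.672.

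**6. Residue that recurs in the same subject.** Section 5.5.3 tells subjects to keep their adhesive routine unchanged, so recurrence is at least as plausible as a random pattern. A lift L at all four visits leaves period-minus-subject baseline unchanged and moves all four AOB0-12 values by −0.979 L. For a subject with complete data this cancels from every treatment difference.

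**7. Continuance.** A lift of L lb takes out only a subject whose clean baseline lies within L lb of the 9 lb limit. A lift equal across the day's four pre-treatment bites cancels in the 2 lb rule. At Visit 2 the check comes before randomization, so a failure there is a screen failure and costs no randomized data; recurring residue would mostly show at that visit. A failure at Visit 3 costs three of four periods. Against that, 45 is a minimum, and the schedule in SAP 3.1 holds sequences for 60 subjects.

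**The case for a change.** The case for acting is that the sponsor itself treats upper denture cleaning as a separate step at screening, so its absence from 8.2.1 is a real gap. Section 9.2 sends the efficacy assessments to that very list, and footnote 6 ties the Visits 2-5 cleaning to a later moment. End-of-day cleaning may be with warm water only, so residue is plausible. A correction costs one line, and Amendment 1 already removed another 8.2.1 entry because it did not fit the rest of the protocol.

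The textual part stands: the list is incomplete, and neither footnote 6 nor 8.1.5 fills the gap. The possibility of an avoidable discontinuation at Visits 3-5 also stands, though nothing in the documents lets it be quantified. What does not follow is that the plan needs changing. The step is already required by 4.1, and a low cost of correction does not show that the result depends on it. The largest loss above, about 0.94 to 0.90, needs a 4 lb lift in half of all subject-periods against a 9 lb ceiling, with full carry-over, at a site that disregards 4.1.

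**Conclusion.** This is a clerical omission in one procedure list, and no change to the plan follows. A site that reads the whole protocol cleans the upper denture before the baseline bite. If a site did not, the omission would apply equally to all four treatments and bias no comparison. The cost would be extra baseline noise, most of which the planned covariate removes: at most about 4% on the SE for an assumed 2 lb lift and 8% for 4 lb, with study success still near or above the stated 90%. If the residue recurs within subjects, the treatment contrasts of complete subjects do not move.

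The sizes rest on assumed lifts, frequency, baseline SD and carry-over, because the documents supply none. The conclusions that the passages are compatible and that the contrasts are unbiased do not depend on those sizes. The no-bias conclusion needs only that residue on arrival is unrelated to the treatment assigned for that day. The list could be aligned with 4.1 whenever the protocol is next amended, but no analysis or conclusion depends on it.
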